11.2.1 Analysis Populations

The *intention-to-treat* (ITT) population shall be defined as the population of all enrolled subjects who were assigned to a study group and who experienced a minimum of one severe or very severe headache within 4 weeks of enrollment. This population shall include subjects who were non-compliant with study procedures, and subjects who were assigned to the incorrect device specific to their study group.

The *per-protocol* population shall be defined as the population of all enrolled subjects who were assigned to the correct device specific to their study group, who experienced a minimum of one severe or very severe headache within 4 weeks of enrollment, and who were compliant with study procedures throughout the duration of their enrollment in the study.

Analyses of the primary and secondary endpoints shall be conducted using data from intention-to-treat population. Analyses of exploratory endpoints shall be conducted using data from the per-protocol population.

² Olsen MF, Bjerre E, Hansen MD *et al.* Pain relief that matters to patients: systematic review of empirical studies assessing the minimum clinically important difference in acute pain. *BMC Medicine* 2017, 15: 35.

³ Farrar JT, Young JP Jr., LaMoreaux L *et al.* Clinical importance of changes in chronic pain intensity measured on an 11-point numerical pain rating scale. *Pain* 2001, 94: 149-158.

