4.3 Exploratory Endpoints

Exploratory endpoint variables are:

- The proportion of subjects who report mild or no symptoms (defined as a pain score of 3 or less) after an elapsed time of 2 hours following application of the device, with respect to their first severe or very severe migraine headache;
- The proportion of subjects who require abortive medication to control their first severe or very severe migraine headache within 8 hours following application of the device; and
- The proportion of subjects who report sensitivity to light after elapsed times of 2 hours and 4 hours following application of the device, with respect to their first severe or very severe migraine headache.

5. Inclusion/Exclusion Criteria

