6.4 Procedures and Assessments

Subjects will be directed to:

- apply the study glasses at the first onset of aura, or as soon as possible once they experience symptoms consistent with the onset of a migraine attack.
- avoid taking abortive medication for the first four hours of a migraine attack. If abortive medications cannot be avoided, the subject should document use.
- record the following information for the first (and all subsequent) severe or very severe migraine headaches that they experience while enrolled in the study:
 - The date and time of symptom onset;

¹ Kwong WJ and Pathak DS. Validation of the eleven-point pain scale in the measurement of migraine headache pain. *Cephalgia* 2007; 27: 336-342.

- The pain score (as assessed on the 11-point pain scale) just prior to the application of the study glasses (score needs to be greater than or equal to 6 to qualify as a severe or very severe headache);
- The time at which the study glasses are applied;
- Whether the subject was wearing prescription eyewear in addition to the study glasses, or whether the study glasses alone were worn;
- The pain score (as assessed on the eleven-point pain scale) 2 hours after the study glasses are applied;
- The pain score (as assessed on the eleven-point pain scale) 4 hours after the study glasses are applied;
- The type of abortive medication taken (if any) to control headache symptoms, the dosage taken, and the time at which the medication is taken; and
- Any experience of light sensitivity within 4 hours after the study glasses are applied, and the time at which light sensitivity is first experienced.

Subjects will participate in the study for a maximum of four (4) weeks \pm 3 days after enrollment; if a given subject does not experience a severe or very severe migraine headache within four (4) weeks, that subject will not be included in the evaluable study population.

Study coordinators will contact subjects once per week to ensure they are wearing the study device as instructed, and that they are recording the requested information related to their headaches. These weekly contacts will also enable coordinators to identify and address any barriers to adherence with the protocol.

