11.2.3 Handling of Missing Data

In the intention-to-treat population, any missing pain scores at time points of 2 and 4 hours after application of the device shall be imputed using a multiple imputation procedure, with study arm, age, sex, baseline pain score, number of severe or very severe headaches experienced while enrolled in the study, and pain scores at 2 and 4 hours after application of the device for subsequent severe or very severe headaches experienced while enrolled in the study as predictors. Imputation procedures shall utilize predictive mean matching.⁴ A total of 50 sets of multiple imputations shall be generated; the analysis of the primary endpoint shall be conducted for each set, and a pooled estimate of the difference in mean improvement between the two devices will be computed, along with a 95% interval estimate and p -value associated with the null hypothesis.

In the per-protocol population, subjects with a missing value of an exploratory endpoint will not be included in the evaluable population for that endpoint.

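### Exploratory endpoints are scored on the first severe headache but analysed only in subjects compliant for the whole enrolment, so a later lapse discards an outcome already known

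*Combined protocol and SAP*

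**What the plan says.** Section 4.3 ties the exploratory endpoints to one headache. Response at 2 hours and light sensitivity at 2 and 4 hours are taken "with respect to their first severe or very severe migraine headache", and the abortive-medication endpoint covers the 8 hours after device application for that same headache. Each outcome is therefore settled within 8 hours of applying the device.

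Procedures continue after that. Section 6.4 tells subjects to "record the following information for the first (and all subsequent) severe or very severe migraine headaches", over up to four weeks.

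Section 11.2.1 defines two populations. Both require subjects "who experienced a minimum of one severe or very severe headache within 4 weeks of enrollment". Of the ITT set it says: "This population shall include subjects who were non-compliant with study procedures". The per-protocol set also requires the correct device and admits only subjects "who were compliant with study procedures throughout the duration of their enrollment in the study". Primary and secondary endpoints go to ITT. For the rest: "Analyses of exploratory endpoints shall be conducted using data from the per-protocol population". No ITT version of the exploratory analyses is given.

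Section 11.2.3 drops subjects with a missing exploratory value from that endpoint. Section 11.2.7 specifies a stratified Cochran-Mantel-Haenszel test and a pooled odds ratio with an exact interval.

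**The concern.** The compliance window is longer than the endpoint window. A subject who follows every instruction at the first severe headache, but misses a diary entry at the third, leaves the analysis although the outcome was recorded and cannot be changed by the later lapse. Subjects with more headaches have more chances to be removed.

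The plan itself expects repeat headaches. Section 5.1 requires at least two severe attacks in the month before entry, and Section 11.2.3 uses the number of on-study headaches, and the scores "for subsequent severe or very severe headaches experienced while enrolled in the study as predictors", to impute missing pain scores.

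Two things are at stake. Precision is lost for reasons unrelated to the scored headache. The randomised comparison may also be distorted if those who lapse differ in outcome between arms. Some related ITT evidence exists: the primary endpoint uses the same 2-hour score, and Section 11.2.5 compares rescue use within 2 hours of symptom onset. The 8-hour medication endpoint is covered only in part by that comparison, and light sensitivity has no close ITT counterpart.

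**Working it through.** **The plan's own figures.** Section 11.1 gives 27 per arm for 95% power (difference 2, SD 2.0, two-sided 0.05). A two-sample t-test with 27 per arm has power 0.950. Allowing for 20% dropout, 27/0.80 = 33.75, so 34 per arm and 68 in total. These reproduce and are unaffected. No figure is given for the exploratory endpoints or the per-protocol set, and no lapse, response or on-study headache rate. All rates below are therefore assumptions.

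**Step 1: share removed.** Let c be compliance per headache, independent across headaches, and k the number of qualifying headaches. Among subjects compliant at the first headache, the share removed by later lapses is 1 − c^(k−1).

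| c | k = 2 | k = 4 |
|---|---|---|
| 0.95 | 5.0% | 14.3% |
| 0.90 | 10.0% | 27.1% |
| 0.80 | 20.0% | 48.8% |

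**Step 2: precision.** The interval for the log odds ratio widens by the factor 1/√(c^(k−1)). At c = 0.90 this is 1.054 for k = 2 and 1.171 for k = 4.

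Take assumed response rates of 50% and 20%, so the odds ratio is (0.5/0.5)/(0.2/0.8) = 4.0. The standard error of the log odds ratio is the square root of the sum of 1/cell over the four expected cells, and the large-sample 95% interval is 4.0 × exp(±1.96 × SE). At c = 0.90, treating the starting number as first-headache compliers:

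| Per arm at start | k | Retained per arm | SE | 95% interval |
|---|---|---|---|---|
| 27 | none lost | 27 | 0.62 | 1.20–13.4 |
| 27 | 2 | 27 × 0.90 = 24.3 | 0.65 | 1.12–14.3 |
| 27 | 4 | 27 × 0.729 = 19.7 | 0.72 | 0.97–16.5 |
| 34 | none lost | 34 | 0.55 | 1.36–11.7 |
| 34 | 4 | 34 × 0.729 = 24.8 | 0.64 | 1.13–14.1 |

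**Step 3: bias.** Let l be the lapse rate, with R for responders and N for non-responders. Then

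observed OR = true OR × [(1 − l_R,active)(1 − l_N,sham)] / [(1 − l_N,active)(1 − l_R,sham)].

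The base rate is 10% in every cell, and the non-responder rate is then raised:

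| Non-responder lapse rate | Factor | True OR 4.0 becomes | True OR 1.0 becomes |
|---|---|---|---|
| raised equally in both arms | 1 | 4.0 | 1.0 |
| 20%, sham only | 0.80/0.90 = 0.889 | 3.56 | 0.89 |
| 20%, active only | 0.90/0.80 = 1.125 | 4.50 | 1.13 |
| 30%, sham only | 0.70/0.90 = 0.778 | 3.11 | 0.78 |
| 30%, active only | 0.90/0.70 = 1.286 | 5.14 | 1.29 |

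Neither the direction nor the size of any real bias can be determined from the documents.

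**The case against.** The strongest reply is that compliance is undefined. Section 11.2 promises a SAP before database lock; if it counts only major departures, few scored subjects would be lost. That stands as a limit on the likely size. It does not remove the problem, because the per-protocol-only assignment and the whole-enrolment window are already stated and a SAP that follows them inherits both.

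The stakes are low, since no power calculation or main conclusion rests on these endpoints. Blinding (Section 6.2) and weekly contacts (Section 6.4) also make arm-specific lapsing less likely. Both points stand, and they are why the rating is minor. Loss of precision needs no failure of blinding.

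The illustration can be pressed in both directions:

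- The only severe-attack rate in the documents is the entry floor of two in the prior month. With two headaches the interval stays above 1 (1.12–14.3). The limit of 0.97 needs four headaches and 27 per arm, and should be read as an unfavourable case.
- Lapses probably cluster within subjects. Under a beta-binomial model with mean compliance 90%, removal at four headaches falls from 27% to 19% (intraclass correlation 0.2) or 16% (0.3).
- In the other direction, 27 is the evaluable number, not the number compliant at the first headache. Like for like at 90%, retention goes from 27 × 0.90 = 24.3 to 27 × 0.90^4 = 17.7 per arm.
- The intervals above are unstratified and large-sample, whereas Section 11.2.7 asks for a stratified analysis with an exact interval. An unstratified exact interval with 27 per arm and no exclusions already has a lower limit of about 1.04 (13 v 5 responders) or 0.87 (13 v 6). Whether an interval crosses 1 should therefore carry little weight; the relative widening is the better measure.

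Finally, judging compliance at the first headache alone would cure the mismatch. That is true, but it would still leave these endpoints without an analysis that keeps non-compliant subjects.

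**Conclusion.** The concern holds as a minor design point. Read together, Sections 4.3, 6.4 and 11.2.1 discard outcomes that are already known because of events that come after them. Confidence in the mismatch is high because it rests on the text. Its size is uncertain because it depends on assumed lapse rates, headache counts and independence. At 90% compliance per headache the cost is 10% to 27% of first-headache compliers for two to four headaches, less if lapses cluster. Bias is modest unless lapsing is strongly arm-specific, and absent if its relation to response is the same in both arms. Only the exploratory results are affected.

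**What to change.** - Analyse the exploratory endpoints in the Section 11.2.1 ITT population by randomised arm, with the same Cochran-Mantel-Haenszel test.
- Derive 2-hour responder status (score of 3 or less) from the pain scores already imputed for ITT, combined over the 50 sets, with the observed-data result and the Section 11.2.7 exact interval beside it.
- For abortive medication and light sensitivity, use observed data and report the number missing by arm.
- Keep per-protocol as supportive, with compliance judged on the first qualifying headache only and the rule fixed before unblinding.
- State that documented abortive use is not a reason for exclusion from the supportive analysis. Section 6.4 asks subjects to avoid such medication for four hours, then adds: "If abortive medications cannot be avoided, the subject should document use". If that use counted as a lapse, the per-protocol set would select on the second exploratory endpoint; the documents do not settle this. The statement concerns analysis membership only.

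The cost is a short wording change to Section 11.2.1, a matching line in Section 11.2.3 (whose exploratory missing-data rule covers only per-protocol), and a rule in the SAP for combining the Cochran-Mantel-Haenszel result over imputed sets, which the plan now lacks. Programming is minor because the ITT set and imputed scores are already needed for the primary analysis. The estimates will include non-compliant subjects. The ITT set also still requires a qualifying headache after randomisation, so the result is closer to the full randomised comparison but not identical to it.

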11.2.2 Subject Accountability

All subjects who provided informed consent (screened subjects) will be included in a summary of subject accountability. The number of subjects screened, the number and percentage of subjects who were screen failures, and the number and percentage of subjects who were enrolled in the study will be summarized by investigational site and overall. The reasons for screen failure will also be tabulated.

11.2.3 Handling of Missing Data

In the intention-to-treat population, any missing pain scores at time points of 2 and 4 hours after application of the device shall be imputed using a multiple imputation procedure, with study arm, age, sex, baseline pain score, number of severe or very severe headaches experienced while enrolled in the study, and pain scores at 2 and 4 hours after application of the device for subsequent severe or very severe headaches experienced while enrolled in the study as predictors. Imputation procedures shall utilize predictive mean matching.⁴ A total of 50 sets of multiple imputations shall be generated; the analysis of the primary endpoint shall be conducted for each set, and a pooled estimate of the difference in mean improvement between the two devices will be computed, along with a 95% interval estimate and p -value associated with the null hypothesis.

In the per-protocol population, subjects with a missing value of an exploratory endpoint will not be included in the evaluable population for that endpoint.

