11.1 Sample Size Justification

A pilot evaluation of the Avulux® and control/sham devices (n = 10 subjects using each type of device) demonstrated that users of the Avulux® device reported a mean decrease of 4.1 points in pain score (standard deviation = 1.9 points) after an elapsed time of 2 hours, and users of the placebo device reported a mean decrease of 1.9 points in pain score (standard deviation = 1.5 points) after an elapsed time of 2 hours. The difference between the performance of the two devices was statistically significant ($p = 0.004$).

Assuming that subjects with severe or very severe migraine headaches achieve a mean 4-point improvement in pain score when using the investigative device and at most a mean 2-point improvement when using the control/sham device, and assuming a standard deviation of at

most 2.0 points when estimating the mean difference in pain scores in individual study subjects after application of either device, a sample size of 27 subjects per study arm provides a minimum statistical power of 95% to detect a significant difference in mean results for the primary endpoint variable between the two (2) device types, at a significance level of $\alpha = 0.05$. Given an estimated dropout rate of up to 20% in each study arm, a minimum of 34 subjects per arm (or 68 total subjects) are required to be enrolled in this study.

The above assumptions imply that the mean improvement in pain score after 2 hours will be at least 2 points higher for the Avulux® device than for the control/sham device. Meta-analyses have shown that the minimal clinically important difference (MCID) to detect changes in acute pain as measured on the 11-point pain scale is 1.7 points;^{2,3} therefore, a 2-point difference in mean improvement between study devices is considered to be clinically meaningful.

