11.2 Proposed Analyses

A statistical analysis plan, containing detailed information regarding the proposed statistical analyses of study data, will be created and approved prior to database lock.

Unless otherwise stated, all statistical testing will be two-sided and will be performed using a significance level of $\alpha = 0.05$.

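### The imputation model in 11.2.3 does not list the index headache's other score or rescue use, and gives no rule for later-headache scores that do not exist

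*Combined protocol and SAP*

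**What the plan says.** Section 11.2.3 (Handling of Missing Data) states that in the ITT population "any missing pain scores at time points of 2 and 4 hours after application of the device shall be imputed" by multiple imputation with predictive mean matching and 50 sets. The reference given for the method is on chained equations. The listed predictors are arm, sex, age, baseline score, the number of severe headaches on study, and 2-hour and 4-hour scores "for subsequent severe or very severe headaches experienced while enrolled in the study as predictors".

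Four other places bear on this list:

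- Section 11.2.1 admits a subject to the ITT population after one severe headache. A later headache is not required.
- Section 6.4 has the subject record both post-application scores of each severe headache and, for any abortive drug, its type, dosage and "the time at which the medication is taken".
- Section 11.2.5 treats early rescue use as a possible influence on the primary endpoint. It compares the arms on rescue within 2 hours of symptom onset and moves to an ANCOVA if they differ significantly. Section 11.2.6 follows the same route at 4 hours.
- Section 11.2 defers detail to a SAP to be approved before database lock.

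**The concern.** An imputation model should contain the variables of the analysis model and the recorded variables most likely to explain both the missing score and why it is missing. The listed set falls short in three ways.

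1. **The other score of the same headache is not listed.** When a 2-hour score is missing and the 4-hour score was recorded, the 4-hour score is direct evidence of how that headache went. The list names post-application scores only for later headaches.
2. **Rescue use is not listed.** If the ANCOVA is triggered by rescue use, the analysis model holds a covariate that the imputation model lacks. Imputed scores then carry no association with rescue beyond what the other predictors bring, which tends to weaken the adjustment.
3. **Some listed predictors cannot exist.** A subject with one severe headache has no later score. Chained equations would either impute a score for a headache that never happened or need an unwritten rule. The text also does not say how two or more later headaches enter the model.

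The pooled imputation result is the primary result, so two statisticians working from the same text could report different primary estimates.

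**Working it through.** **1. The plan's own figures.** Section 11.1 assumes that subjects "achieve a mean 4-point improvement in pain score when using the investigative device and at most a mean 2-point improvement", with an SD of at "most 2.0 points when estimating the mean difference in pain scores in individual study subjects", and concludes that "a sample size of 27 subjects per study arm provides a minimum statistical power of 95" percent. With a difference of 2, SD 2 and two-sided alpha 0.05:

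- Normal approximation: n = 2 × (1.960 + 1.645)² × 2² / 2² = 26.0, so 26 per arm.
- Exact t-test power: 94.2% at 26 per arm and 95.0% at 27.
- Dropout: 27 / 0.80 = 33.75, so 34 per arm.

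These figures reproduce and are not affected by this point. The documents give no figure for missing scores.

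**2. ITT subjects with no later headache.** The headache rate is not in the documents. Assume a Poisson count with mean m per 4 weeks. Among subjects with at least one severe headache, the share with exactly one is m·e^(-m) / (1 - e^(-m)).

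| Assumed mean | Share with one only |
|---|---|
| 2 | 0.271 / 0.865 = 31% |
| 3 | 0.149 / 0.950 = 16% |
| 4 | 0.073 / 0.982 = 7.5% |

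At mean 2, about 18 of 59 ITT subjects (from 68 enrolled) would have no later score. Overdispersed counts give 33%, 21% and 13% at means 2, 3 and 4.

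**3. Bias when missingness follows rescue use.** Simulation with 34 per arm, 400 trials per scenario, predictive mean matching, 20 imputations, and later scores imputed where none exists. Assumed correlations are 0.7 between the 2-hour and 4-hour scores and 0.4 between headaches. The full-data effect is about 1.9 after rounding to the 0-10 scale. Bias is measured against full data, with Monte Carlo error of about 0.01 to 0.02. The last column adds the index 4-hour score and rescue use.

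| Scenario (all rates assumed) | Listed predictors | With both added |
|---|---|---|
| (a) Missingness unrelated to rescue, 15% missing | -0.02 | -0.02 |
| (b) Missing 40% with rescue, 7% without; rescue 15% active, 45% control; rescue goes with scores 1.5 higher | -0.14 | -0.07 |
| (c) Stronger: 60% and 5%; rescue 10% and 50%; scores 2 higher | -0.33 | -0.11 |
| (d) As (b), but scores 1.5 lower | +0.07 | -0.02 |
| (e) As (b), but rescue 30% in both arms | -0.04 | -0.04 |

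In (c), adding only the 4-hour score leaves -0.21, and adding only rescue use leaves -0.11. Rescue use does most of the work under this mechanism.

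**4. Bias when missingness follows the course of the headache.** Again 34 per arm, with a true difference of 2.00 and the 4-hour score observed. Missingness of the 2-hour score rises with a poor course in the active arm only. The listed predictors gave 2.26, an excess of 0.26 / 2.00 = 13%. Across assumed 2-hour/4-hour correlations of 0.6 to 0.8 and 17% to 22% missing, the estimate was 2.25 to 2.30. Adding the same-headache 4-hour score returned it to 2.0. With random missingness, or missingness tied to course equally in both arms, there was no material bias.

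**5. Precision.** In (a), the mean standard error was 0.511 with the listed predictors and 0.501 with the additions (0.511 / 0.501 = 1.02). The course-driven setting gave a standard error about 3% to 5% larger than needed.

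**6. Consequence for the test.** In (c), the worst case, the mean estimate under the listed predictors is 1.555 with mean standard error 0.564, and 1.555 / 0.564 = 2.8. At the planned effect, the estimate is affected more than the finding of a difference.

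**The case against.** The strongest reply is that omission of the other index score is an ambiguity. Both index scores are imputation targets and the cited method is chained equations, in which one target can predict another. The list can be read as additional to the targets, and a detailed SAP is still to come. This stands in part. A reader might infer that the plan excludes the same-headache score, and the documents do not say that. They do not say that it is included either, and a predictor set built from the text as written would leave it out. The reply does not cover rescue use, which is not a target.

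The bias also needs particular conditions. Nothing in the documents shows missingness that differs by arm; subjects are blinded and contacted weekly about recording. This stands, and it limits the size of the point.

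The 4-hour score cannot help a subject who lacks both index scores. For that subject, any later-headache scores would be the only post-baseline pain data. This stands, and it is a reason to keep the later-headache information in some form. No simulation isolated harm from imputing later scores that do not exist, so that part of the point rests on logic and on the absent rule.

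The amount missing may be smaller than simulated. Section 11.1 says "Given an estimated dropout rate of up to 20% in each study arm, a minimum of 34 subjects per arm", which is 0.20 × 34 = 6.8 per arm. If that allowance also covers subjects with no severe headache, who are outside ITT, then at an assumed Poisson mean of 2 they take 0.135 × 34 = 4.6 of it. That leaves 2.2 of 29.4 ITT subjects per arm, or 7.5%.

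**Conclusion.** The point holds as a gap in the imputation model with a conditional effect. As listed, the model omits rescue use, which the diary records and the ANCOVA may use. It leaves the role of the other index score unstated, and it has no rule for subjects without a later headache.

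Read literally, the cost is a standard error about 2% to 5% larger and a possible bias in either direction of up to about 0.3 points on a 2-point effect. The larger values need missingness linked to the headache's course differently by arm, or linked to rescue use that itself differs by arm. Otherwise the bias is not material. For scale, section 11.1 cites an MCID of 1.7, which is 0.3 below the assumed difference.

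All rescue rates, missingness rates, correlations and headache counts are assumptions. A reader might infer that the effect will be overstated by 12% to 15%, that many subjects lack later scores, or that the listed predictors are weak. The documents support none of these. They give no missingness pattern, headache rate or correlation, and the simulated bias took both signs. Entry requires at least two severe attacks in the prior month, which makes a mean near 2 plausible but does not establish it.

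**What to change.** In section 11.2.3 and the SAP:

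- State that the index 2-hour and 4-hour scores are imputed jointly, each predicting the other.
- Add abortive medication use and its timing as predictors (before the 2-hour score, before the 4-hour score), coded so that the early-use variable of section 11.2.5, which counts from symptom onset, is also in the model. The diary times allow both.
- Replace the individual later-headache scores with one summary, such as the mean change over later severe headaches, plus an indicator for having any later headache. Set the summary to a fixed value when there is none, so that no score is imputed for a headache that did not occur.
- Keep the other predictors, predictive mean matching and 50 sets.

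The cost is wording only. Every variable is already collected and the sample size stands. The downsides are one or two more terms in a small-sample imputation model and some loss of detail from the later headaches. The change reduces rather than removes the bias in the harder rescue scenarios (-0.33 to -0.11 in (c)).
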